## 7 Statistical Plan

### General Considerations

**Continuous data** (e.g., age) will be summarized using the following descriptive summary statistics: the number of subjects (n), mean, SD, median, minimum value (min), and maximum value (max). For each continuous variable, the corresponding mean, median, minimum and maximum will be presented to 1 decimal place and the SD to 2 decimal places, unless otherwise specified.

**Categorical variables** (e.g., qualitative presence of absence of Ga-DOTATATE) will be summarized using counts and percentages. Percentages will be presented to 1 decimal place. Summaries of continuous and categorical data will be presented, as appropriate.

**Incomplete/Missing data:** Missing data (e.g., dates, post-baseline values) will not be imputed, unless otherwise specified; i.e., all missing values and missing post-baseline values will remain as missing in all statistical analyses and listings, unless otherwise specified.

**Outliers:** No formal statistical analyses will be performed to detect and/or remedy the presence of statistical outliers.

Additionally, all subject data, including derived variables, will be presented in subject data listings; listings will display all subjects who were randomized or enrolled in the study.

#### 7.1.1 Background Characteristics

##### 7.1.1.1 Demographics and Baseline Characteristics

Demographics and baseline characteristics (age, sex, race, ethnicity, weight, height and body mass index [BMI]) will be summarized.

#### 7.1.2 Efficacy Analysis

##### 7.1.2.1 Analysis of Primary Efficacy Endpoint

Nominal continuous variables will be represented as the mean +/- SD and categorical variables will be noted as the number and percentage of total. Pearson chi-square test will be utilized to determine statistical significance for continuous variables whereas a Student's two-sample t-test will be implemented to determine statistical significance for continuous variables. Univariate and

multivariate analyses will be performed when relevant. Statistical significance will be set a priori as a p-value less than 0.05. Concordance and discordance of Ga-DOTATATE with FDG and NH3 PET/CT for the presence or absence of CS will be calculated and utilizing FDG PET/CT as the “gold-standard” for CS, the sensitivity and specificity of Ga-DOTATATE for the detection of CS will be determined. Given that this is a pilot study no power calculation will be performed. All statistical analyses will be performed using JMP Pro 9 (SAS Institute INC. Cary, North Carolina).

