### **3.1 Study Endpoints**

1. Assess utilizing both qualitative and quantitative methods the myocardial Ga-DOTATATE uptake in patients with and without active CS as determined by FDG and NH3 PET/CT.
2. Determine the concordance and discordance of Ga-DOTATATE with FDG and NH3 PET/CT for the presence or absence of CS utilizing FDG and NH3 PET/CT as the “gold-standard” for CS. Determine the sensitivity and specificity of Ga-DOTATATE for the detection of CS will be determined.
3. Calculate physician confidence in study interpretation for both Ga-DOTATATE and FDG and NH3 PET/CT.
4. Compare patient satisfaction between the FDG and NH3 PET/CT and Ga-DOTATATE protocols.
5. Utilize information obtained from the current pilot as a foundation to pursue potentially larger trials.

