## **4 Subject Selection and Withdrawal**

### **4.1 Inclusion Criteria**

- 1) 18 years of age or older
- 2) Referred for and undergo clinically indicated FDG PET/CT scan for CS
- 3) Have clinically suspected, or newly diagnosed CS
- 4) Are able to complete both the clinically indicated FDG and NH3 PET/CT and the Ga-DOTATATE scan and do so within one month of each other without the introduction of CS directed therapy between the scans

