#### 6.1.2 Analysis of PET data

Once the cardiac PET/CT images are obtained they will be assessed for the presence of CS utilizing similar methodologies which were previously published (1,2,24).

Qualitative assessment of FDG and NH3 PET/CT and Ga-DOTATATE for each study subject will be made by two different study investigators (JB and AK) who will be blinded to the patient clinical history, laboratory data and any other imaging assessment (including the corresponding CS study-i.e. when reading the Ga-DOTATATE study investigators will be blinded to the FDG results and vice versa) at the time of interpretation. For both FDG and Ga-DOTATATE cardiac uptake study investigators will classify the patient into one of four categories of radionuclide uptake: none, diffuse, focal, and focal on diffuse or diffuse. The portions of the myocardium that demonstrate uptake will be documented in accordance with the 17 segment American Heart Association model (28). In concordance with national guidelines(24), FDG and Ga-DOTATATE examinations will be interpreted simultaneously with NH3 to allow for assessment of myocardial perfusion. Both FDG and Ga-DOTATATE studies will then be labeled as positive for CS, negative for CS or inconclusive.

Any discordance between the findings of the two investigators in regards to the presence or absence of CS as well as the extent will be reviewed by additional investigators (GJ or PC) and final determination in regards to classification of the patient will be made.

Semiquantitative determination of radionuclide uptake will be determined by using commercially available software to calculate maximum standard uptake value (SUVmax) of FDG and Ga-DOTATATE in the heart. This data will be correlated with patient clinical data obtained from the medical record.

The two study investigators (JB and AK) who are reviewing all studies will rank their confidence level for interpretation for each scan on a 5 point scale (1=least confident, 5= most confident). Results will then be compared between the two study modalities.

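### Reader confidence and patient ease are paired within patient, but the only tests named are for independent groups, and no rule combines the two readers' confidence scores

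*Combined protocol and SAP*

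**What the plan says.** - **Design.** Section 4.1 admits patients who "Are able to complete both the clinically indicated" FDG/NH3 scan and the DOTATATE scan within a month of each other. Section 3 sets the number at 15, and Section 4.3.1 does not replace withdrawals, so 15 pairs is the maximum.
- **Endpoints (Section 3.1).** Endpoint 3 is to "Calculate physician confidence in study interpretation for both" imaging approaches. Endpoint 4 is to "Compare patient satisfaction between the" two protocols.
- **Confidence (Section 6.1.2).** Two readers "who are reviewing all studies will rank their confidence level for interpretation for each scan on a 5 point scale", and "Results will then be compared between the two study modalities". That gives four scores per patient.
- **Ease (Section 6.1.2, patient survey).** Each patient scores the ease of each study from 1 to 5, then says which study was preferred, with equality as a permitted answer.
- **Reader disagreement (Section 6.1.2).** "Any discordance between the findings of the two investigators in regards to the presence or absence of CS as well as the extent" goes to further investigators. Confidence scores are not covered.
- **Tests (Section 7.1.2.1 and the Study Summary).** "Pearson chi-square test will be utilized to determine statistical significance for continuous variables whereas a Student's two-sample t-test will be implemented". The sentence goes on to give the t-test to continuous variables too, so its first *continuous* is evidently a slip for *categorical*. The threshold follows: "Statistical significance will be set a priori as a p-value less than 0.05".

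Univariate and multivariate analyses are mentioned without detail. No paired t-test, signed-rank, McNemar, mixed or clustered method is named.

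**The concern.** The plan's rule picks a test by variable type alone. Followed literally, it sends two sets of scores from the same 15 patients to a test that treats them as two separate groups. That test's standard error ignores the within-patient correlation, so its nominal 5% is not its real error rate.

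Confidence has a second layer. With two readers per scan, an analyst could average the scores, analyse each reader separately or pool them. Pooling treats two readings of one scan as independent, which works in the opposite direction to ignoring positive pairing.

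At stake are the study's two comparisons of reader confidence and patient experience, which endpoint 5 would carry into larger trials. The two-sample t-test is appropriate for endpoint 1 (uptake in patients with versus without active disease). Concordance, sensitivity and specificity are descriptive and are not affected.

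**Working it through.** The plan has no power calculation, so it gives no figure to reproduce.

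**Inputs.** From the documents: 15 patients, two tracers, two readers, 5-point scores, threshold 0.05. Assumed, because the documents give none: a two-sided test, the correlations, and a shift of 0.8 SD for power.

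**1. One value per patient per tracer.** With SD 1 and within-patient correlation r:

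- SE used by the two-sample t-test: √(2/15) = 0.365
- True SE: √(2(1−r)/15) = 0.306, 0.258 and 0.200 at r = 0.3, 0.5 and 0.7
- Mean difference needed for p<0.05, unpaired (28 df): 2.048 × 0.365 = 0.75 SD
- Mean difference needed, paired (14 df): 2.145 × √(2(1−r)/15), tabulated below

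Error rates and power come from 200,000 simulated normal trials per row.

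| r | Paired difference needed (SD) | Type I error, two-sample | Power, two-sample | Power, paired |
|---|---|---|---|---|
| −0.3 | 0.89 | 8.5% | 56% | 43% |
| 0 | 0.78 | 5.0% | 56% | 53% |
| 0.3 | 0.66 | 2.1% | 57% | 68% |
| 0.5 | 0.55 | 0.8% | 58% | 82% |
| 0.7 | 0.43 | 0.1% | 61% | 96% |

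The paired t-test's type I error is 5.0–5.1% in every row. At r = −0.3 the higher unpaired power comes with an inflated error rate.

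**2. Five-point scores.** Cutting the normal values into scores 1 to 5 changes little. Over the same five correlations, type I error is 8.2 / 5.2 / 2.3 / 1.1 / 0.3% for the two-sample t-test, 4.7–5.2% for the paired t-test, and 4.0 / 3.9 / 3.0 / 2.8 / 2.2% for the exact signed-rank test, which ties make conservative. Power at 0.8 SD is 52–54% for the two-sample t-test, 41 / 50 / 62 / 75 / 89% for the paired t-test and 37 / 43 / 55 / 66 / 82% for signed-rank.

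**3. Two readers pooled as 30 versus 30.** Let ri be the correlation between readers on the same scan and rc the correlation across tracers.

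- Variance of the mean difference that the test assumes: 2/30 = 1/15
- True variance: (1 + ri − 2rc)/15
- Ratio, true to assumed: 1 + ri − 2rc

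The pooled test is therefore anti-conservative when ri > 2rc and conservative when ri < 2rc. Simulated type I error, 58 df:

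| ri / rc | Ratio | Type I error, pooled two-sample |
|---|---|---|
| 0.8 / 0.7 | 0.4 | 0.5% |
| 0.7 / 0.5 | 0.7 | 2.5% |
| 0.5 / 0.3 | 0.9 | 4.2% |
| 0.5 / 0.2 | 1.1 | 6.5% |
| 0.8 / 0.3 | 1.2 | 8.2% |
| 0.7 / 0.2 | 1.3 | 9.1% |
| 0.8 / 0.2 | 1.4 | 10.5% |

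Over all 12 combinations run, the range is 0.5% to 10.5%.

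**4. Does naming a paired test suffice?** No. A paired t-test on 30 reader-level pairs gives 6.5% to 14.3% over the same 12 combinations (12.7% at 0.7/0.2), because the two differences from one patient are counted as independent. Averaging the readers first and then pairing over 15 patients gives 4.9% to 5.1%.

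**The case against.** The strongest reply is that the plan prescribes no wrong test. The sentence sits under the primary-endpoint heading and is mapped to nothing. Endpoint 3 speaks only of calculating confidence, and a comparison can be descriptive, for which Section 7 provides summary statistics. On that reading the gap is an unspecified analysis. This is a fair account of the text, but it leads to the same edit: a p<0.05 rule by variable type is stated, nothing else covers endpoints 3 and 4, and an analyst following the plan would reach for the two-sample t-test.

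Pooling the readers is likewise hypothetical, and the grid above uses one cross-tracer correlation. A reader who is habitually confident would correlate more with himself or herself across tracers than with the other reader. The ratio is then 1 + ri − r(same reader) − r(different reader). At 0.5/0.5/0.3, 0.5/0.6/0.3 and 0.3/0.5/0.2 (inter-reader / same reader / different reader) the pooled error is 2.2%, 1.6% and 1.4%, which is conservative. So 0.5–10.5% illustrates rather than bounds the problem. In those same three settings the reader-level paired t-test still gives 9.8%, 11.0% and 7.4%, while averaging and then pairing stays at about 5%.

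Correlation may also be low. The burden of FDG imaging is the diet that DOTATATE is meant to avoid, so the two ease scores may be weakly related. At zero the two-sample t-test is valid and slightly more powerful.

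Finally, this is a 15-patient pilot, and these endpoints are not its stated objective. That limits the consequence. However, Section 7.1.2.1 uses pilot status only to omit a power calculation; it keeps the significance threshold.

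**Conclusion.** The concern holds and should be fixed. The scores are paired, the only named tests assume independence, and confidence has no reader rule. If the two-sample t-test is used on one value per patient per tracer, it is too conservative under positive correlation (0.8% at r = 0.5, with power of 58% against 82% for an assumed 0.8 SD shift) and too liberal under negative correlation (8.5% at −0.3). If readers are pooled, the error can go either way even when all correlations are positive.

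Confidence is high that the mismatch exists. The sizes rest on assumed correlations and an assumed shift, and the documents favour no particular value. The consequence is modest: the per-patient listings in Section 7 keep a paired analysis possible, but both the test and the reader rule would be chosen with the data in view.

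**What to change.** In Section 7.1.2.1 and the Study Summary:

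1. State that confidence and ease are compared between tracers by one paired test, named in advance, on one value per patient per tracer. For confidence, that value is the mean of the two readers. A paired t-test or an exact Wilcoxon signed-rank test on the within-patient differences would serve.
2. State that the two-sample t-test is for endpoint 1, patients with versus without active disease.
3. Correct the first *continuous* to *categorical*.

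Optionally, test stated preference by an exact binomial among patients who state one, reporting the equal answers separately. For example, 3 equal answers leave 12 patients: 10 of 12 gives p = 2(66 + 12 + 1)/4096 = 0.039, and 9 of 12 gives p = 2(220 + 66 + 12 + 1)/4096 = 0.15.

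**Cost.** Wording only, with the same patients, visits and data. Pairing gives up some power if the correlation is zero (53% against 56%) or negative. Signed-rank is conservative on 5-point scores (type I error 2.2–4.0%) and less powerful than the paired t-test. Per-reader analyses or a mixed model would also be defensible; what matters is that one choice is fixed beforehand.

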Statistical Methodology	
Primary Efficacy Analysis: Nominal continuous variables will be represented as the mean +/- SD and categorical variables will be noted as the number and percentage of total. Pearson chi-square test will be utilized to determine statistical significance for continuous variables whereas a Student's two-sample t-test will be implemented to determine statistical significance for continuous variables. Univariate and multivariate analyses will be performed when relevant. Statistical significance will be set a priori as a p-value less than 0.05. Concordance and discordance of Ga-DOTATATE PET/CT with FDG and NH3 PET/CT for the presence or absence of CS will be calculated and utilizing FDG and NH3 PET/CT as the “gold-standard” for CS, the sensitivity and specificity of Ga-DOTATATE for the detection of CS will be determined. All statistical analyses will be performed using JMP Pro 9 (SAS Institute INC. Cary, North Carolina).
 
Safety: The overall safety profile will be assessed in terms of imaging agent related adverse events, and vital signs.

-------------------------	---

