### 3 Study Design

The proposed investigation is a feasibility study designed to assess the efficacy of Ga-DOTATATE PET/CT imaging in the CS population. We propose imaging 15 consecutive patients initially (with an intention to do a larger study) with the standard of care approach of both FDG and NH3 PET/CT and a research Ga-DOTATATE PET/CT. The study group will include adult patients who undergo assessment in Mayo Clinic's CS clinic and have suspected or newly diagnosed CS based upon clinical evaluation. A typical proposed timeline of events for each patient processed through the study is as follows (note exact timeline may vary based on patient appointment schedule):

- 1) *Up to 4-6 weeks prior to visit:* Patient charts will be reviewed prior to their initial appointment in the CS clinic. After review, the physician head of the CS clinic (LB) will refer candidates that have clinically suspected (7), or newly diagnosed CS and who will be referred for a clinically indicated FDG and NH3 PET/CT to the primary investigator (JB). JB or other designated staff will contact the potential study candidates via phone or email (using a phone/email script) to determine their potential interest in the study. If the patient expresses an interest in the study, a consent form will be sent in advance for their review. Patients may consent remotely if they choose or can also be consented in-person. Potential study subjects will also be notified that they will be contacted during their visit for participation in the study.
- 2) *Day 1:* During their FDG and NH3 PET/CT assessment, potential study candidates who have not been consented will be approached by the study coordinator to inquire about their participation in the study. If the patient meets all criteria and agrees to participate in the study, then written consent will be obtained at that time.

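### Section 7.1.2.1 and the Study Summary assign both named tests to continuous variables and none to categorical ones; changing one word would still leave a large-sample test in a 15-patient study

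*Combined protocol and SAP*

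**What the plan says.** The sentence on testing stands in section 7.1.2.1, Analysis of Primary Efficacy Endpoint. Its first half reads "Pearson chi-square test will be utilized to determine statistical significance for continuous variables whereas a Student's two-sample t-test will be implemented"; read through to its end, its second clause says "a Student's two-sample t-test will be implemented to determine statistical significance for continuous variables". The Statistical Methodology row of the Study Summary has the same wording ("Pearson chi-square test will be utilized to determine statistical significance for continuous variables"), so neither place corrects the other.

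Categorical variables are only described. In 7.1.2.1, "categorical variables will be noted as the number and percentage of total"; under General Considerations in section 7 they "will be summarized using counts and percentages". No test for them is named anywhere, yet 7.1.2.1 sets a significance threshold of 0.05 in advance.

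Concordance, discordance, sensitivity and specificity against FDG PET/CT are to be calculated or determined. No test, agreement statistic or confidence interval is attached to them.

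On size and design, section 3 says "We propose imaging 15 consecutive patients initially", and section 4.3.1 rules out replacing withdrawn subjects. Section 4.1 requires patients to be able to complete the clinical scans and the DOTATATE "scan and do so within one month of each other without the introduction of CS directed therapy between the scans". The two modalities are therefore compared within patients.

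**The concern.** Taken literally, the rule cannot be carried out: a chi-square test does not apply to a continuous measurement such as SUVmax, and an analyst with a categorical comparison has no instruction. The obvious repair is to read the first *continuous* as *categorical*. That makes the sentence coherent but leaves three matters open.

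- Pearson's test relies on a large-sample approximation, and there are at most 15 patients.
- The main categorical result is a paired table of DOTATATE label by FDG label. A test of association is not a test of agreement.
- The t-test in the same sentence is the two-sample (unpaired) one, while reader confidence and patient ease ratings (section 6.1.2) are two scores from the same patient.

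What is at stake is modest but real. A 0.05 threshold is declared, the choice of test at this size can decide which side of it a result falls on, and section 3.1 makes the pilot a foundation for larger trials.

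**Working it through.** **Plan's own figure.** The sample size of 15 has no derivation, and 7.1.2.1 states that no power calculation is made. There is nothing to reproduce.

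**Inputs.** N = 15 (section 3); threshold 0.05 (section 7.1.2.1), taken as two-sided because sidedness is not stated. The documents give no expected prevalence, so splits are assumed and shown as a range. The 2x2 figures assume no inconclusive scans.

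**1. Expected counts.** The smallest expected count in a 2x2 table is (smaller row total × smaller column total) / N. It is largest when the margins are 7 and 8: 7 × 7 / 15 = 3.27. The usual rule of thumb asks for 5, which first becomes attainable at N = 20 (10 × 10 / 20 = 5).

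**2. True size of uncorrected Pearson at nominal 5%.** For each split into two independent groups with a common event rate p, add the binomial probabilities of all tables with chi-square above 3.84, then take the maximum over p:

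| Split | Pearson, maximum size | Fisher, maximum size |
|---|---|---|
| 2/13 | 5.6% | 0.9% |
| 3/12 | 8.9% | 1.8% |
| 4/11 | 5.1% | 1.7% |
| 5/10 | 5.0% | 2.8% |
| 6/9 | 4.3% | 3.5% |
| 7/8 | 4.6% | 3.5% |

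The 3/12 peak comes mainly from one table: a single event, in the group of three. Its chi-square is 15 × (1×12 − 2×0)² / (3 × 12 × 1 × 14) = 2160/504 = 4.29, which is significant. At p = 0.08 its probability is 3 × 0.08 × 0.92^14 = 0.075. Fisher's p for that table is 3/15 = 0.20.

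**3. How often the choice matters.** Of the 236 possible 2x2 tables of 15 with Pearson p < 0.05, 72 (72/236 = 31%) have Fisher p ≥ 0.05. This counts tables without weighting them by probability.

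**4. Association against agreement.** Tables are (both positive, FDG only, DOTATATE only, both negative):

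| Table | Agreement | Pearson p | Fisher p | Exact McNemar p |
|---|---|---|---|---|
| 7, 0, 0, 8 | 15/15 | 0.0001 | 0.0002 | 1.0 |
| 0, 7, 8, 0 | 0/15 | 0.0001 | 0.0002 | 1.0 |
| 2, 3, 0, 10 | 12/15, sensitivity 2/5 = 40% | 0.032 | 0.095 | 0.25 |
| 5, 6, 0, 4 | 9/15 | 0.099 | 0.23 | 0.031 |

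The first two rows are opposites, yet each test gives them the same p. Pearson and Fisher test association; McNemar tests whether discordance runs in one direction. None of the three measures agreement.

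**5. Unpaired t-test on paired scores.** With equal variances and within-patient correlation ρ, the standard error of the mean difference is √(2σ²/n) unpaired and √(2σ²(1−ρ)/n) paired, a ratio of 1/√(1−ρ). For assumed ρ of 0.3, 0.5 and 0.7 the unpaired error is 1.20, 1.41 and 1.83 times the paired one.

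**6. What exact intervals would show.** Clopper-Pearson 95%: 5/5 gives 47.8–100%, 7/7 gives 59.0–100%, 10/10 gives 69.2–100%; for concordance, 15/15 gives 78.2–100% and 14/15 gives 68.1–99.8%.

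**The case against.** The strongest reply is that this is a slip of one word. The sentence contrasts two tests, the sentence before it pairs continuous with categorical variables, and nobody would run a chi-square on SUVmax. That is a fair account of how the error arose. It does not remove it, because it stands uncorrected in both places, and the one-word repair leaves the points above.

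A reader might go further and infer that the plan will apply Pearson to the DOTATATE-by-FDG table and present a p-value below 0.05 as support for DOTATATE. The documents do not support this. Agreement and accuracy are only to be calculated; the two-by-two examples show what would happen if Pearson were used there, not what is planned. Sensitivity and concordance are prespecified outputs, so 40% sensitivity or 0% agreement would be visible whatever the p-value.

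A reader might also conclude that Pearson fails at 15 patients. That is too strong. Its size is close to nominal for splits from 4/11 to 7/8, the 8.9% is a worst case over an unknown event rate at one uneven split, and the expected count of 5 is a rule of thumb. Nor is Fisher a free improvement: it is conservative, and it tests association just as Pearson does.

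Finally, this is a feasibility pilot with no decision tied to a p-value. That limits the harm, but does not justify leaving a contradictory rule beside a declared threshold.

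**Conclusion.** The point stands as a should-fix. The wording error is certain, appears in both places and has no correction elsewhere. Beyond it, the most that can be said is that the Pearson approximation is unreliable for uneven splits, with true size up to about 8.9% among splits from 2/13 to 7/8, and that no exact or paired method is named although the sample is small and both scans are done in each patient.

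The point on agreement is conditional: it bites only if the chi-square is carried over to the paired table. What the plan lacks there is an interval and a statement that the comparison is descriptive.

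The size figures assume two-sided testing, independent groups and 15 evaluable patients with definite labels. Section 6.1.2 allows inconclusive readings, and section 1.1 cites up to 30% for FDG; 0.30 × 15 = 4.5 patients, so the evaluable number could be well below 15 and the label table is really 3x3.

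**What to change.** Replace the testing sentence in section 7.1.2.1 and in the Study Summary with text to this effect:

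- Categorical variables compared between independent patient groups: Fisher's exact test.
- Continuous variables compared between independent patient groups: Student's two-sample t-test, for that use only.
- Scores given to both modalities in the same patient, such as reader confidence and ease ratings: a paired method, for example the Wilcoxon signed-rank test.
- DOTATATE against FDG: show the full 3x3 table of positive, negative and inconclusive; report concordance, sensitivity and specificity descriptively with exact 95% confidence intervals and stated denominators. Do not use Pearson or Fisher as a test of agreement. Use exact McNemar only if the direction of discordance is to be tested.

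This costs a few sentences in two places and needs no new patients or data; the methods are standard in statistical software. The downside is that Fisher's test is conservative at this size (true size at most about 3.5%), so p-values will usually be larger, and the exact intervals will be visibly wide.
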